## ***2.7 Liraglutide***

Liraglutide is an acylated human GLP-1RA with 97% amino acid sequence homology to the endogenous form of GLP-1(7-37). It was approved for use in type 2 diabetes in 2009.

Liraglutide, like other GLP-1RAs, increases intracellular cyclic AMP in  $\beta$ -cells leading to insulin release in the presence of elevated glucose concentrations; thus, insulin secretion subsides as blood glucose decreases and approaches euglycemia [10]. The clinical implication of this is that hypoglycemia is infrequent when liraglutide is combined with agents other than sulfonylureas or insulin. Liraglutide also decreases glucagon secretion in a glucose-dependent manner, but does not limit the  $\alpha$ -cell's response to hypoglycemia. The mechanism of blood glucose lowering may also involve a delay in gastric emptying. Unlike native GLP-1, liraglutide is stable against metabolic degradation by dipeptidyl peptidase-4 (DPP-4) and neutral endopeptidases.

$\beta$ -cell function in patients with type 2 diabetes is enhanced by liraglutide therapy either alone or in combination with other glucose lowering agents [61]. In animal studies, beneficial effects on  $\beta$ -cell mass have also been observed, but such an effect in humans has not been demonstrated. Liraglutide is also associated with reductions in body weight.

Liraglutide is associated with upper gastrointestinal side effects including nausea and vomiting, which frequently subside with continued treatment and can be reduced in severity by dose titration. GLP-1 based therapies, which would include liraglutide, have been reported to be associated with an increased risk of pancreatitis, the mechanism for which is unclear [62]. This adverse effect occurs on a background of an increased risk of pancreatitis in patients with type 2 diabetes [63]. In rodent studies, liraglutide has been found to cause thyroid C-cell tumors; however, it has not been established that this occurs in humans [62]. Given the above, liraglutide should not be used in patients with a history of pancreatitis, a personal or family history of medullary thyroid carcinoma or in patients with multiple endocrine neoplasia syndrome type 2.

## ***2.8 Approaches to Measuring $\beta$ -cell Function, $\alpha$ -cell Function, Insulin Sensitivity and Glucose Tolerance***

Glucose homeostasis is physiologically modulated under fasting and prandial conditions by a number of regulatory factors, most prominently insulin and glucagon. Measurements made under fasting conditions are generally proportional to direct measures of the dynamic responses, but the most rigorous measurement of  $\beta$ -cell function (insulin and/or C-peptide responses to physiologic stimuli) comes from evaluation of dynamic tests. Dynamic testing can be accomplished with oral intake of glucose or mixed meals, or with intravenous infusion of glucose or other  $\beta$ -cell stimulators. In RISE, the hyperglycemic clamp technique will be used to examine insulin sensitivity and  $\beta$ -cell function, and the OGTT will be used as a complementary measure that more closely reflects the integrated physiologic response to ingested stimuli, including incretins.

### ***2.8.1 Intravenous Tests of $\beta$ - and $\alpha$ -cell Function and Insulin Sensitivity***

Glucose tolerance is dependent on  $\beta$ -cell function and insulin sensitivity, and both of these can be quantified using the hyperglycemic clamp [64]. The role of  $\alpha$ -cell function in determining glucose tolerance is less well defined.

The acute insulin (C-peptide) response to intravenous glucose (AIRg or first phase insulin response) occurs within the first ten minutes following bolus glucose administration and is a sensitive marker of  $\beta$ -cell function that decreases as the fasting glucose level rises. A potential “drawback” of this measure is that the first phase response drops sharply as the fasting glucose level approaches 115 mg/dl [65]. Above that level, the first-phase response is markedly diminished and frequently absent. Although this early response may respond to treatment interventions aimed at restoring or preserving  $\beta$ -cell function in some patients, this defect, in the absence of medication, appears particularly resistant to reversal. The response is possibly

**CONFIDENTIAL**

related to the type of intervention used to bring about improvement in  $\beta$ -cell function. These difficulties with measuring early responses at baseline limit our ability to depend on this measure of  $\beta$ -cell function as a primary outcome in RISE.

The second phase insulin response to intravenous glucose begins at the time of glucose administration and continues for as long as the glucose level remains elevated. It is frequently quantified as part of a hyperglycemic clamp. Unlike the acute insulin response to glucose, the second phase response persists and is measurable even when the fasting glucose concentration exceeds 115 mg/dl [66]. Moreover, it is proportional to overall  $\beta$ -cell secretory capacity and can be measurably improved with treatment interventions targeting  $\beta$ -cell function [67].

$\beta$ -cells also respond to non-glucose secretagogues, such as peptides and amino acids. The prevailing glucose level modulates the  $\beta$ -cell secretory response to non-glucose secretagogues. By performing hyperglycemic clamps with the addition of a bolus intravenous arginine injection, it is possible to quantify the maximum insulin response (AIRmax), which provides an estimate of the maximum  $\beta$ -cell secretory capacity at a given point in time. In the absence of techniques that provide a direct measure of  $\beta$ -cell mass in living humans, this measure of maximal secretory capacity is currently taken as an indirect measure of  $\beta$ -cell mass. AIRmax is decreased in patients with type 2 diabetes [30] and in those at risk of developing the disorder [68]. Again, unlike the first phase response, AIRmax responses are present and readily quantified in individuals with higher fasting glucose levels ( $>115$  mg/dl). Effects of treatment interventions on AIRmax have not been extensively evaluated but are beginning to be studied [56].

$\beta$ -cell responses also are modulated by the prevailing insulin sensitivity. Therefore, expressing  $\beta$ -cell function relative to insulin sensitivity provides a better estimate of how well the  $\beta$ -cell is performing [69]. This approach of accounting for the effect of insulin sensitivity has been used extensively with AIRg derived from frequently sampled IV glucose tolerance tests, where the intravenous glucose tolerance test (IVGTT)-derived measure of insulin sensitivity ( $S_I$ ) is used to produce the 'disposition index' ( $S_I \times AIRg$ ) [69]. This approach can also be applied to adjust other measures of  $\beta$ -cell function, providing that the underlying assumption of a hyperbolic relationship between the insulin sensitivity variable and the  $\beta$ -cell function variable is true. Likewise, AIRmax can be adjusted for insulin sensitivity (e.g.  $S_I \times AIRmax$ ; [69]). Insulin sensitivity-adjusted  $\beta$ -cell function measures derived from second phase responses and AIRmax responses measured with hyperglycemic clamp methods have been selected as the primary outcome measurements for RISE.

The reciprocal of glucose's ability to potentiate the  $\beta$ -cell response is its ability to suppress glucagon secretion from the  $\alpha$ -cell. This function can also be measured using hyperglycemic clamps along with arginine [30, 70]. The ability of glucose to suppress the acute glucagon

**CONFIDENTIAL**

response is impaired in people with type 2 diabetes and in those with prediabetes, indicative of impaired  $\alpha$ -cell regulation [30, 71]. This parameter will be quantified using the hyperglycemic clamp with arginine injection (AGRmin, minimum acute glucagon response) and, if funding is available, will be analyzed as a secondary outcome in RISE.

### ***2.8.2 Oral Tests of $\beta$ - and $\alpha$ -cell Function and Insulin Sensitivity***

The OGTT provides measures of islet function and has been used in large clinical trials for this purpose. The early insulin response (insulinogenic index) is an important determinant of glucose tolerance [18]. This response, when used in combination with a fasting measure of insulin sensitivity (1/fasting insulin, HOMA, or QUICKI) provides another estimate of  $\beta$ -cell function termed the “oral disposition index” (DIO) [22, 72]. However, the accuracy of HOMA in assessing changes in insulin sensitivity over time may not be as reproducible and accurate as clamp techniques [73]. Using modeling approaches such as those developed by Mari et al. [74] and Cobelli et al. [75], it is possible to obtain a number of additional parameters of  $\beta$ -cell function and insulin sensitivity from the OGTT. In addition, using C-peptide levels and deconvolution techniques, insulin secretion rates can be calculated from the OGTT [74-76]. Finally, overall glucose tolerance can be calculated from the glucose excursion during the test [77], providing a measure that is directly interpretable and applicable in the clinical setting.

Physiological glucagon suppression during an OGTT is an important determinant of glucose tolerance and provides an estimate of  $\alpha$ -cell function. In individuals with type 2 diabetes, glucagon suppression is impaired [2, 28, 29], an abnormality that is improved with incretin-based therapy [10]. However, whether this change persists after withdrawal of therapy is unknown.

These OGTT-based measures will be performed in the study and their relationship with intravenous test-based measurements will be determined, both at baseline and following drug interventions.

### ***2.9 Biomarkers of $\beta$ -cell Function, $\alpha$ -cell Function, Insulin Sensitivity and Glucose Tolerance***

It is often the case that biologic phenomena of interest are both difficult and costly to measure directly. This can be true of physiologic states such as  $\beta$ -cell function, but it is also true for time-dependent changes such as rates of progression to overt diabetes. In these instances we turn to biomarkers. An optimal biomarker is measured from a single biological sample (e.g., blood or urine) and is less costly, less labor intensive and highly correlated with the result from the process under evaluation. However, a biomarker might be the result of combinations of blood

**CONFIDENTIAL**

tests, or measurements from other body fluids, or even measurements of other biological substances [78].

In RISE, treatments aimed at restoring or preserving  $\beta$ -cell function are being implemented and their effects determined using dynamic measures of  $\beta$ -cell function discussed above. This provides the opportunity to concurrently attempt to identify biomarkers to assess islet function in relation to the systemic metabolic state, and to predict how these change over time. The identification of such biomarkers is an important ancillary goal of the project since a practical application of strategies learned from this study will ultimately require a screening test to identify likely responders to the interventions.

### **2.9.1 Putative Diabetes Biomarkers**

The detailed measures of  $\beta$ -cell function that we will be making provide an opportunity to identify biomarkers that can predict deterioration of  $\beta$ -cell function and/or response to interventions that can mitigate such deterioration. The identification of such biomarkers is an important ancillary goal of the RISE Consortium. Because of budget constraints, the focus during this stage of the project will be on collecting patient specimens that can be used in the future for identification of biomarkers once the main outcomes of the study are known. We will collect samples that can be used to examine previously described peptide markers of diabetes risk (e.g., adiponectin, ferritin, ApoB, C-reactive protein, IL-2 receptor A [79-82]) and evolving markers of  $\beta$ -cell mass regulation (e.g., prolactin, DNA fragments and methylation, GLP-1, glucose-dependent insulinotropic peptide [GIP], HSP90nucleic acids [83-87]). We will also collect serum samples that can be analyzed using genomic, micro-RNA, proteomic and metabolomics approaches comparing for example responders to non-responders to the study interventions.

## **3 STUDY DESIGN**

### **3.1 Overview and Rationale**

This document is specific for the RISE Adult Medication Protocol that three centers are performing together in individuals with prediabetes or recent onset type 2 diabetes. This preliminary proof-of-principle study is a randomized, partially blinded, placebo-controlled trial comparing metformin alone, insulin glargine followed by metformin, or liraglutide plus metformin to placebo. The primary outcome is  $\beta$ -cell function, measured as defined below.

The RISE Adult Medication Protocol will involve 255 adults age 20-65 years old. Volunteers will be men and women with prediabetes or with drug-naïve, recent onset, mild type 2 diabetes who meet the following glucose-based parameters: HbA1c  $\leq 7.0\%$ , plus an OGTT fasting plasma

**CONFIDENTIAL**

glucose 95-125 mg/dl and a 2-hour post challenge glucose  $\geq$ 140 mg/dl. Participants will be randomized to: (1) metformin alone for 12 months, (2) 3-months basal insulin glargine titrated to normalize fasting glucose followed by 9 months metformin, (3) liraglutide plus metformin for 12 months, or (4) placebo for 12 months. Volunteers will be recruited over a three-year period and followed for a total of 21 months following randomization. After baseline assessments and the run-in period, participants will be treated with active medication or placebo for 12 months. To determine if treatment has persistent benefits on  $\beta$ -cell function, subjects will be followed after discontinuation of treatment for a minimum of 3 months and up to 9 months if possible. Primary and secondary assessments will be performed at various time intervals while participants are receiving therapy and after medication discontinuation. The timing of the study, including interventions and testing, is shown in Figure 1.

[figure not shown]

Figure 1: Timing of interventions and outcomes testing for RISE Adult Medication Protocol

The chosen interventions are intended to test whether “resting” the  $\beta$ -cell (metformin alone or metformin following normalization of fasting glucose with long-acting insulin) or “improving”  $\beta$ - and  $\alpha$ -cell function (liraglutide) will retard the natural progression of prediabetes and type 2 diabetes. A placebo arm is included as a control group to determine the effects of the interventions relative to the natural history of the disease.

By including a 3-month washout period after which the primary outcomes will be assessed, the study will examine whether a beneficial effect of treatment persists beyond the period of active drug intervention. While shorter initial treatment intervals may be effective, the plan is first to determine the efficacy and durability of 12 months of treatment as a proof of principle. If no sustained effect is seen after 12 months of treatment, then it is very unlikely that a shorter treatment period would be efficacious. Complete end-of-study measures will be performed at the end of the 3-month washout period (15 months on study) and used for the primary analysis of the study. Where possible,  $\beta$ -cell function will be measured using an OGTT at 9 months post therapy (21 months on study) to evaluate whether treatment effects persist beyond the initial

**CONFIDENTIAL**

3-month washout period. Full evaluation of the length of any durable response beyond these time points will require future studies designed specifically to address that question.

### **3.2 Primary Outcomes**

The primary objective of the RISE Study is to evaluate the effects of randomized treatment on  $\beta$ -cell function, measured by hyperglycemic clamp techniques. Given that insulin and C-peptide are both used in quantifying  $\beta$ -cell function, each of them will be measured in certain or all tests in part to avoid the problem of collinearity when performing the statistical analyses.

Two co-primary outcomes are specified:

- $\beta$ -cell function measured as the **second phase response (steady-state of the hyperglycemic clamp)** (100-120 minutes of glucose infusion) [64]. This will be calculated as mean C-peptide at steady state, adjusted for insulin sensitivity using the hyperglycemic clamp-derived measure of insulin sensitivity (glucose disposal rate/insulin: GDR/I).
- $\beta$ -cell function measured as **AIRmax (arginine-induced acute insulin response at hyperglycemic glucose;  $\beta$ -cell secretory capacity)** [30]. This will be calculated as the incremental area under the C-peptide curve from 0-10 minutes following arginine injection at a plasma glucose  $\geq 450$  mg/dl, adjusted for insulin sensitivity measured by the hyperglycemic clamp.

Overall, for primary and secondary outcomes we will use the insulin sensitivity measured during steady state of the hyperglycemic clamp (glucose disposal rate [derived from the steady state glucose infusion rate] divided by steady state plasma insulin concentration 100-120 min) for adjustment of  $\beta$ -cell function measures [69].

The main analysis will evaluate the effect of study treatments to induce durable improvement in these primary outcome measures of  $\beta$ -cell function, by comparing each treatment against placebo following a 3-month medication washout. The study will be analyzed under the intention-to-treat principle.

### **3.3 Secondary Outcomes**

There are a number of pre-specified secondary outcomes. These include measures derived from the hyperglycemic clamp that are not specified as primary outcomes; measures derived from the OGTT; analyses related to treatment effect at the end of the 12 month active intervention period compared to pre-treatment baseline; and analyses related to various putative predictors of treatment outcome.

**CONFIDENTIAL**

As presented in Figure 1, the timing of available secondary measures differs according to measurement methodology. Secondary outcomes will be evaluated by intention-to-treat analyses when evaluating effects of randomized study treatments.

### **3.3.1 $\beta$ -cell Function and Glucose Tolerance**

- (i) Hyperglycemic clamp-derived  $\beta$ -cell measures:
  - a. First phase insulin response (incremental insulin area from 0-10 minutes after initial glucose bolus)
  - b. First phase C-peptide response (incremental C-peptide area from 0-10 minutes after initial glucose bolus)
  - c. Disposition index derived from a and b, adjusting for insulin sensitivity using the hyperglycemic clamp-derived measure of insulin sensitivity (glucose disposal rate/insulin: GDR/I)
  - d. Second phase insulin response, with adjustment for insulin sensitivity using non-clamp-derived surrogate measures
  - e. AIRmax response to arginine calculated using insulin concentrations and adjusted for insulin sensitivity
- (ii) OGTT-derived  $\beta$ -cell measures:
  - a. Early insulin response to oral glucose (insulinogenic index:  $\Delta$  insulin from 0-30 minutes/ $\Delta$  glucose from 0-30 minutes [ $\Delta$ I/ $\Delta$ G])
  - b. Early C-peptide response to oral glucose (parallel to (a))
  - c. Oral disposition index (Dlo; insulinogenic index adjusted for insulin sensitivity)
  - d. Modeled parameters of  $\beta$ -cell function ( $\beta$ -cell glucose sensitivity, rate sensitivity and potentiation factor; static, dynamic, and total  $\beta$ -cell glucose sensitivity)
  - e. Ratios of incremental insulin/glucose (iAUCins/iAUCg) and C-peptide/glucose (iAUCc-p/iAUCg) responses from 0-120 minutes
  - f. Incremental glucose (iAUCg) response as a measure of glucose tolerance
  - g. 2-hour glucose
  - h. GLP-1 total and incremental response to oral glucose load (samples will be collected, and measured for this analysis if funding allows)
- (iii) Fasting measures:
  - a. Glucose
  - b. Proinsulin/insulin ratio
  - c. HOMA %B (using the Oxford calculator)
  - d. HbA1c

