RISE Primary Outcome Analysis Plan – Adult Medication Study

Approved by RISE Steering Committee, Sept 2017

Approved by RISE DSMB, November 2017

Often the Disposition Index (DI) – insulin sensitivity * insulin response – is used as an overall measure of beta-cell function that appropriately accounts for the reciprocal relationship of insulin sensitivity and the beta-cell's insulin response. In these analyses, the DI assumes that the product of the two variables is constant within an individual at a given time, such that changes in insulin sensitivity would be mirrored by a proportional change in the insulin response. This implies that all points along the line represent the same level of metabolic function. In many instances this relationship has been demonstrated using insulin responses to be a rectangular hyperbola (by definition, the slope of the log-log relationship equal to -1.0); however, in others this relationship has just been assumed. The power calculations for RISE were based on the DI using data provided by several investigators that used methodologies that differed from those used in RISE.

During protocol development there was thus concern that relationships underlying this constant depend on the actual measures of peptide (insulin or C-peptide) release by the beta cell. In particular, the slope of the log-log relationship between secretion and sensitivity might not be equal to -1.0 for the C-peptide measures chosen for RISE as had been observed in prior studies based on insulin measures. Therefore, the protocols specifically state that the primary outcomes would be based on two different C-peptide responses (steady state and maximal) adjusted for insulin sensitivity defined as the glucose disposal rate divided by steady state insulin (aka M/I) during the hyperglycemic clamp. However, given the likely possibility that the relationship may not be a rectangular hyperbola, the protocol did not specify details of the approach to be used for the primary outcome analysis as a decision would be based on evaluation of the baseline data.

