During analysis of the baseline data, we found that the DI (i.e. sensitivity x secretion) is sometimes paradoxically lower in pediatric participants than adult participants, despite the fact that the insulin sensitivity vs. C-peptide curves describing the relationship between these two variables appears higher in children. This contradictory finding is at least in part due to the fact that the range of values for insulin sensitivity among children is narrow compared to that of adults, i.e., children are more insulin resistant than adults. Further, the log-log slopes of insulin sensitivity vs. C-peptide responses are not equal to -1 in children or adults (or overall). Although the untransformed data show a clear inverse relationship typical of a hyperbolic curve, the slopes for each of the primary outcome measures on the log scale is approximately -0.3 (not -1.0 as may have been expected); this is a hyperbola but not a square hyperbola. Thus, the approach of performing the primary outcome analysis comparing treatment groups after washout, with a test of difference in DI at Month 15 adjusted for baseline, may not be appropriate and needed to be reassessed.

Several options were considered including a simple linear regression model (on a log scale) of C-peptide (and insulin) release as a function of insulin sensitivity, with a term for treatment group and adjusting for both variables at baseline. However, this was also deemed inappropriate because that model would estimate the difference in C-peptide (and insulin) release between groups assuming that there was no difference in insulin sensitivity between groups. Rather, we want to account for movement of both variables simultaneously without forcing a specific relationship between them. This can be accomplished by performing the primary outcome analysis using two separate models: insulin sensitivity at Month 15 vs. treatment arm (adjusted for baseline) and C-peptide (and insulin)

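### The first-phase C-peptide disposition index keeps a product form that the SAP abandoned for the C-peptide primary outcomes, and no slope check or alternative is specified for any secondary disposition index

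*Protocol*

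**What the plan says.** Protocol 3.3.1 lists, among the clamp-derived secondary outcomes, item (i)c: "Disposition index derived from a and b, adjusting for insulin sensitivity using the hyperglycemic clamp-derived measure of insulin sensitivity" (GDR/I, which the SAP calls M/I). Items a and b are first-phase insulin and first-phase C-peptide, so (i)c gives two indices, one based on each peptide. Item (ii)c is an oral disposition index, described as "insulinogenic index adjusted for insulin sensitivity".

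Protocol 2.8.1 introduces the disposition index as sensitivity times acute response. It allows the approach for other secretion measures "providing that the underlying assumption of a hyperbolic relationship between the insulin sensitivity variable and the" secretion variable is true. The SAP's opening paragraph defines the index as "insulin sensitivity * insulin response" and ties the constant-product property to a rectangular hyperbola, meaning a log-log slope of -1.

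The SAP then reports the baseline data: "the log-log slopes of insulin sensitivity vs. C-peptide responses are not equal to -1 in children or adults", nor overall, and "the slopes for each of the primary outcome measures on the log scale is approximately -0.3". It doubts that a Month 15 test of the disposition index is suitable. It replaces that test, for the primary outcomes, with two baseline-adjusted equations (sensitivity and secretion) fitted jointly, and a 2-df test. If that test is significant, a further look at how each variable moved within each arm follows.

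Protocol 9.2 sends secondary continuous outcomes to baseline-adjusted ANCOVA with the closed testing procedure. Neither document revisits (i)c or (ii)c in the light of the slope finding.

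**The concern.** A disposition index is meant to separate a change in beta-cell function from the ordinary adjustment of secretion to sensitivity. It does so only if secretion falls in exact inverse proportion when sensitivity rises. If secretion falls by less, a participant who simply moves along an unchanged curve gets a higher index when sensitivity rises and a lower one when it falls. An arm difference in sensitivity could then be read as an arm difference in beta-cell function.

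The SAP recognises the general problem: it notes that both variables can move along a shared curve with no underlying change in function, and it adds a follow-up step for the primary outcomes. The secondary product index has no such safeguard. Some movement in sensitivity is plausible, at least on treatment. Protocol 2.5 describes metformin improving sensitivity and lowering insulin release in an earlier prevention trial, and Protocol 2.7 notes weight loss with liraglutide. The Month 12 comparison is a stated secondary aim.

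**Working it through.** **Inputs**
- Baseline log-log slope b of C-peptide response on sensitivity: about -0.3 for each of the two primary measures (SAP). No data, standard error or interval is given, so it cannot be recomputed.
- Slope at which the product is constant: -1 (SAP, opening paragraph).
- Slopes for first-phase C-peptide, first-phase insulin and OGTT responses: not given. I use a range from -0.3 to -1.
- Size of the sensitivity change: not given. Changes of -20%, +20% and +50% are illustrations.

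**Effect of a compensated change on the product**

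Let S be sensitivity and R the response, and let the participant stay on one curve, R = c × S^b. Then the index is S × R = c × S^(1+b), and a k-fold change in S multiplies it by k^(1+b).

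At b = -0.3 and k = 1.2, the response is multiplied by 1.2^(-0.3) = 0.947 and the index by 1.2 × 0.947 = 1.2^0.7 = 1.136, a rise of 13.6%. The same formula gives:

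| Slope b | S falls 20% | S rises 20% | S rises 50% |
|---|---|---|---|
| -0.3 | -14.5% | +13.6% | +32.8% |
| -0.6 | -8.5% | +7.6% | +17.6% |
| -0.8 | -4.4% | +3.7% | +8.4% |
| -1.0 | 0% | 0% | 0% |

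As a check, an index whose exponent matches the slope, S^0.3 × R at b = -0.3, changes by a factor of 1.2^0.3 × 1.2^(-0.3) = 1, so it does not move.

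**Could a test pick this up as benefit?**

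This needs the residual SD of the log index, which the documents do not give; I assume 0.3 to 0.8. Take 56 per arm (Protocol 9.3), one pairwise two-sided test at 0.05 on the log scale, and a compensated 20% gain in one arm.
- Slope -0.3: the shift is 0.7 × ln 1.2 = 0.128, or 0.43 to 0.16 SD. The chance of a significant difference in the favourable direction is 62% at SD 0.3 and 13% at SD 0.8.
- Slope -0.6: the shift is 0.4 × ln 1.2 = 0.073, or 0.24 to 0.09 SD. The chance is 25% to 7%.
- Slope -1: the shift is 0 and the chance is the nominal 2.5%.

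The closed procedure requires the four-arm and three-arm tests to be significant as well, so it cannot raise these figures.

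**The case against.** Several points on the other side stand, and they limit the concern.

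- **The -0.3 slope belongs to other measures.** It is reported for steady-state and arginine-stimulated C-peptide. Using it for first-phase C-peptide is extrapolation, although the SAP's general sentence on C-peptide responses does point away from -1. It is also a baseline slope across participants; within-person change may follow another slope.
- **Insulin-based indices may be sound.** A reader might infer that every secondary disposition index is biased. The documents do not support that. The insulin half of (i)c and the oral index as defined rest on insulin, for which the SAP says a rectangular hyperbola has been shown in many instances.
- **Not every adjustment is written as a product.** The oral index is only called adjusted. Reading that as regression on sensitivity gives no refuge, though, because the SAP also rejects that model: it assumes equal sensitivity across arms. Item (i)c uses the defined term.
- **Protocol 2.8.1 does not state a slope of -1.** It asks for a hyperbolic relationship; the -1 condition comes from the SAP, which describes the RISE data as hyperbolic but not rectangular.
- **The SAP covers the primary outcome.** Its silence on secondary outcomes is not a decision to keep products there. Its account of the joint model mentions insulin as well as C-peptide release, so the method was evidently seen as usable for both. It still names no first-phase or OGTT measure.
- **Direction is not established.** A reader might infer that the error favours the active arms. The main comparisons come 3 and 9 months after treatment stops, no residual sensitivity gain is documented there, and glargine is associated with weight gain. The paradoxical ordering that the SAP reports was between children and adults, not between treatment arms.
- **Month 21 does not rest on the oral index alone.** A reader might infer this because no clamp is done then. Protocol 3.3.1(ii)d lists modelled beta-cell parameters from the OGTT, and 3.3.3 reports sensitivity separately. A sensitivity shift would therefore be visible, though seeing it does not correct the index.
- **The joint test is not a cure by itself.** The SAP accepts that it can be significant after a mutually compensated shift, so its follow-up step has to come with it.

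**Conclusion.** The point holds for the first-phase C-peptide disposition index. As written, (i)c uses a form that the SAP judged doubtful for C-peptide in this study's own baseline data, and the plan neither checks the slope nor offers an alternative.

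The consequence is conditional: a compensated sensitivity change could, not would, be reported as a change in beta-cell function, with the sign of the error following the sign of the sensitivity change. How large the error is depends on three things that the documents do not give: the first-phase slope, the sensitivity difference between arms, and the residual variability. Across slopes from -0.3 to -0.8, a compensated 20% gain shifts the index by 13.6% down to 3.7%; at -1 there is no error. For the insulin-based and oral indices, the finding is only that the assumption is unchecked in RISE.

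The primary outcomes are not affected. The point is worth settling before the secondary analyses because the remedy is already in the sponsor's own plan.

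**What to change.** Add the following to the SAP.

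1. **First-phase C-peptide.** Replace the product with the SAP's two-equation model: GDR/I and first-phase C-peptide, each adjusted for its own baseline and fitted jointly. Report both arm differences together. Before claiming improved beta-cell function, apply the SAP's follow-up evaluation of how the two variables moved within each arm.
2. **First-phase insulin and the oral index.** Estimate the baseline log-log slope and its confidence interval before looking at arms. Keep the product only where the slope is compatible with -1 and the interval is narrow enough to be informative. Otherwise use the joint approach in step 1. State the formula for the oral index.
3. **Scale.** Protocol 2.8.1 says that the first-phase response is often absent above a fasting glucose of 115 mg/dl, which lies inside the eligible range of 95-125 mg/dl. Increments at or below zero cannot be logged, so specify the raw scale or a stated shift in advance.

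The cost is SAP wording and a little more analysis of data already collected. The drawback is that some secondary outcomes lose a single summary index and need a two-part interpretation.
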